18.2. Adverse Events

18.2.1. Treatment Emergent Adverse Events (TEAEs)

All types of AE summarization described in this section are for TEAEs only, which is defined as AEs that occur or worsen after the first dose of study drug up to the end of the study (Visit Follow-Up 2/Day 43).

Severity is classed as mild, moderate, or severe (increasing severity). TEAEs starting after the first dose of study drug with a missing severity will be classified as severe. If a subject reports a TEAE more than once within the same System Organ Class (SOC) and Preferred Term (PT), then the TEAE with the worst-case severity will be used in the corresponding severity summaries.

Relationship to study treatment, as indicated by the Investigator, is “Unrelated” if the TEAE is “not related” or “unlikely related”. A “related” TEAE is defined as a TEAE with a relationship of “possibly related”, “probably related”, or “definitely related” to study medication. TEAEs with a missing relationship to study medication will be regarded as “related” to study medication.

A TEAE overview summary will be provided for FAS by cohort and for total (Cohort 1 and 2). The following categories will be presented in the AE overview summary:

- Number of subjects with any TEAE
- Number of subjects with any TEAE related to study treatment
- Number of subjects with any SAE
- Number of subjects with any SAE related to study treatment
- Number of subjects with any TEAE leading to study treatment discontinuation
- Number of subjects with any TEAE by highest severity
 - Mild
 - Moderate
 - Severe
- Number of subjects with any AE by strongest relationship with study treatment
 - Related (including definitely related, probably related, possible related, and missing)
 - Unrelated (including unlikely related, not related)

Subject incidence of TEAEs, serious AEs (SAEs), and TEAEs leading to withdrawal of study treatment will be tabulated by SOC and PT in descending order of frequency among the total.

TEAEs that are related to study treatment will be summarized separately. If a subject reports the same TEAE more than once within that SOC/PT, then the TEAE with the worst-case relationship to study treatment will be used in the corresponding relationship summaries.

An AE listing will be provided includes both TEAEs and non-TEAEs.

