### **6.3      Estimated Study Duration**

Each subject will be in the study for up to 55 days. The 55 days are inclusive of an up to 42 days Screening Period followed by a 6-day Treatment Period and a 7-day Washout Period.

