### **6.8      End of Study**

A subject is considered to have completed the study if all phases of the study are completed including the Follow-up Visit (FU1) on Day 13.

The end of the study is defined as the date of the Follow-up Visit (FU1) on Day 13 for the last active subject in the study.

Study staff will contact subjects by phone 30 days (Day 43, FU2) after FU1 to assess for serious adverse events (SAEs) and if the patient was able to resume breastfeeding (if intended).

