#### **10.3.5 Washout Day 13 (+ 3 days)/End of Study (Visit FU1)**

On Day 13, all subjects will be contacted by phone as a post-treatment follow up visit to review:

- adverse event review;
- concomitant medication review;
- confirm subject discarded breast milk produced after the first dose of IMP through Day 13 per subject report;
- instruct subjects they may resume feeding breast milk currently being produced;
- document subject's intent to resume breastfeeding; and
- schedule optional lactation consultant visit for subjects who desire to re-establish breastfeeding.

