#### **13.1.2 Reporting for Adverse Events**

All AEs occurring during the course of the study (starting from signing informed consent to the end of study) will be collected on the AE eCRF. Subjects should be instructed to report any AE that they experience to the Investigator. Investigators should make an assessment for AEs at each visit and record the event on the appropriate AE eCRF.

Wherever possible, a specific disease or syndrome rather than individual associated signs and symptoms should be identified by the Investigator and recorded on the eCRF; however, if an observed or reported sign or symptom is not considered a component of a specific disease or syndrome by the Investigator, it should be recorded as a separate AE on the eCRF. Additionally, the condition that led to a medical or surgical procedure (e.g., surgery, endoscopy, tooth extraction, transfusion) should be recorded as an AE, not the procedure.

Any medical condition already present at screening or baseline should not be reported as an AE unless the medical condition or signs or symptoms present at baseline changes in severity or seriousness at any time during the study. In this case, it should be reported as an AE.

Clinically significant abnormal laboratory or other examination (e.g., ECG) findings that are detected during the study or are present at baseline and significantly worsen during the study should be reported as AEs. The Investigator will exercise their medical and scientific judgment in deciding whether an abnormal laboratory finding, or other abnormal assessment is clinically significant. Significant abnormal laboratory values occurring during the clinical study will be followed until repeat tests return to normal, stabilize, or are no longer clinically significant. Any abnormal test that is determined to be an error does not require reporting as an AE.

Analyses of certain AEs will be performed in this study for reasons either associated with other lipid-lowering therapies or where deemed important based on nonclinical or clinical data. These

events include the following: hepatic events, musculoskeletal events, diabetes and glycemia, hypoglycemia associated with metabolic acidosis, renal impairment, neurocognitive events, atrial fibrillation, and tendon rupture/tendinopathy.

Each AE is to be evaluated for duration, severity, seriousness, and causal relationship to the IMP. For each AE, the following information will be recorded:

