#### **14.4 Safety Analyses**

General safety data in this study includes AEs, clinical laboratory parameters, PEs, vital signs, and body weight.

Treatment-emergent AEs (TEAEs) are defined as AEs that begin or worsen after randomization and the first dose of IMP through Day 13. TEAEs will be summarized by System Organ Class (SOC), Preferred Term, and severity. Serious TEAEs, IMP-related TEAEs, TEAEs leading to withdrawal of IMP, and deaths will be also summarized.

Clinical laboratory parameters including hematology and blood chemistry, PE findings, vital signs, and body weight will be summarized and listed using descriptive statistics.

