
Follow-up Period: On Day 13, all subjects will be contacted by phone as a post-treatment Follow-up Visit (Visit FU1/End-of-Study [EOS]). Breastfeeding may resume after Visit FU1 on Day 13. An optional lactation consultant visit will be scheduled for those subjects who desire to re-establish breastfeeding. On Day 43 (Visit FU2), study staff will contact subjects by phone to assess for SAEs and if the patient was able to resume breastfeeding (if intended).

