7. STUDY DEFINITIONS

7.1. Disposition

Study Completion: Subjects who complete study at the End of Study (EOS) visit are considered as achieving study completion.

Treatment Completion: Subjects who complete the End of Treatment (D6/EOT) visit on *Day 6* are considered as achieving treatment completion.

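### The SAP runs the TEAE window to FU2/Day 43 and calls that the end of the study, while both documents elsewhere end the study at FU1/Day 13 and leave collection of new non-serious events after FU1 unclear

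*SAP*

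**What the plan says.** **TEAE window.** SAP 18.2.1 counts "AEs that occur or worsen after the first dose of study drug up to the end of the study (Visit Follow-Up 2/Day 43"). Protocol 14.4 counts "AEs that begin or worsen after randomization and the first dose of IMP through Day 13".

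**End of study.** Protocol 10.3.5 is headed "Washout Day 13 (+ 3 days)/End of Study (Visit FU1"). SAP 4.1 labels the same contact "Visit FU1/End-of-Study [EOS"], and SAP 7.1 adds that "Subjects who complete study at the End of Study (EOS) visit are considered as achieving study completion". Protocol 6.8 says a subject has completed the study once all phases through FU1 are done. On duration, protocol 6.3 says "The 55 days are inclusive of an up to 42 days Screening Period followed by a 6-day Treatment Period and a 7-day Washout Period". SAP 18.3.1 uses the end-of-study label a third way, for the Day 7 laboratory visit.

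**What is collected.** Protocol 13.1.2 collects all AEs "starting from signing informed consent to the end of study". Protocol 13.2.4 requires SAE reporting until 30 days after completion or discontinuation. Protocol 13.1.5 follows IMP-related AEs still ongoing at completion for up to 30 days. Protocol 10.3.6 and footnote c of SAP Appendix 1 describe the FU2 call as covering SAEs and resumption of breastfeeding. The SAP schedule nevertheless marks the general Adverse event review row at FU2.

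**Precedence.** Protocol 14.1 and SAP 1 let the SAP prevail where the two differ on data analysis.

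**The concern.** The SAP contradicts itself on when the study ends, and its TEAE window runs 30 days past the point to which the protocol commits to collecting all AEs. Four sets of summaries are exposed: any TEAE, related TEAEs, worst severity, and SOC/PT incidence. In each, a low count of non-serious events after FU1 could mean that few occurred or that few were asked about, and the table would not show which. SAP 18.2.1 also counts missing severity as severe and missing relationship as related, so a sparsely recorded late report would enter those rows.

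The SAE rows are not at risk, because SAEs are collected under one rule until 30 days after completion. TEAEs leading to treatment discontinuation are essentially unaffected, because the last dose is on Day 6.

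A smaller problem has the same cause. SAP Appendix 2 imputes partial AE end dates from the EOS or completion date. With EOS at FU1, that can put an end date before onset for an event that starts after FU1.

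**Working it through.** **1. Where the protocol ends the study.** Protocol 6.3 gives a maximum of 55 days. Screening 42 + treatment 6 + washout 7 = 55, so the figure reproduces, and 6 + 7 = 13 puts the end at Day 13. Ending at FU2 would give 42 + 43 = 85 days, or 90 with the +5-day FU2 window. The stated duration fits FU1 only.

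**2. FU2 timing.** Protocol 6.8 and 10.3.6 place FU2 30 days after FU1: 13 + 30 = Day 43, which also reproduces.

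**3. What is provided for after FU1.**

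| Source | Provision after FU1 |
|---|---|
| Protocol 13.1.2 | All-AE collection is stated to run to end of study |
| Protocol 13.2.4 | SAEs reportable for 30 days |
| Protocol 13.1.5 | Related AEs already ongoing are followed for up to 30 days |
| Protocol 10.3.6; SAP Appendix 1, footnote c | FU2 call on SAEs and breastfeeding |
| SAP Appendix 1, column heading | SAE FU |
| SAP Appendix 1, Adverse event review row | Nine marks for nine columns, so FU2 is marked |
| SAP Appendix 1, Concomitant medications row | Eight marks, ending at FU1 |

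The row mark is the only item pointing to a general AE review at FU2. This reading rests on the SAP's copy of the schedule; the protocol's copy should be checked against it.

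**4. Share of the window after FU1.**
- Nominal: (43 − 13)/43 = 30/43 = 69.8%.
- FU1 on Day 16 and FU2 30 days later, on Day 46: 30/46 = 65.2%.
- FU1 on Day 13 and FU2 on Day 48: 35/48 = 72.9%.

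The range is about 65% to 73% if FU2 is at least 30 days after FU1.

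**5. Weight of one subject.** 1/8 = 12.5 percentage points in a cohort; 1/16 = 6.25 points overall.

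**6. How much could depend on ascertainment.** The documents give no AE rate. *Assume* a constant rate r per subject per 30 days. Expected subjects with at least one event, out of 16, over d fully ascertained days is 16 × [1 − exp(−r·d/30)].

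| Assumed r | 13 days | 43 days |
|---|---|---|
| 0.1 | 0.7 | 2.1 |
| 0.3 | 2.0 | 5.6 |
| 0.5 | 3.1 | 8.2 |
| 1.0 | 5.6 | 12.2 |

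Within each row, the true count under partial ascertainment would lie somewhere between the two columns. This shows why the ascertainment rule has to be stated; it does not forecast this trial.

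**7. Appendix 2 example.** Suppose FU1, and so EOS and completion, falls on 10 March (Day 13). An AE starts on 20 March (Day 23) and its end date is recorded as March with the day missing. The end month and year match EOS, so the rule imputes 10 March, 10 days before onset. The branch for a missing day and month needs only the same year as EOS, so it can do the same.

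**The case against.** **The window is already settled.** A TEAE window is an analysis definition, so the precedence clauses make Day 43 govern. This stands. A reader might infer that the SAP's window is invalid because the protocol says Day 13; the documents do not support that. Precedence does not, however, resolve the SAP's disagreement with its own 4.1, and it collects no data.

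**Protocol 6.8 is partly a trial-level date.** The sentence "The end of the study is defined as the date of the Follow-up Visit (FU1) on Day 13" goes on to refer to the last active subject, so by itself it sets no per-subject limit. This also stands. The subject-level support is the completion sentence of 6.8, protocol 10.3.5 and SAP 4.1.

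**FU2 collection may not be contradictory.** A reader might infer a flat contradiction, or that non-serious events are certainly not collected after Day 13. Neither is shown. Footnote c and the SAE FU heading can be read as limiting the row mark, and that row is also marked for Days 8 to 12, when the schedule shows no phone call. On the other side, protocol 13.1.2 does not say collection is *only* to end of study and asks for AE assessment at each visit, and FU2 is a named visit. The fair description is unclear, with the balance favouring SAEs only.

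**Some late non-serious information is captured by rule.** Protocol 13.1.5 follows ongoing related AEs, and SAP 18.2.1 counts worsening. This is correct, which is why the later period is called mainly, not purely, SAE ascertainment.

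**Cutting at FU1 prejudges what FU2 collects.** That would be fair against simply dropping later events. It does not apply if the summaries are split at FU1 and later events are still shown.

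**The Day 7 wording and Appendix 2 are small.** Agreed. SAP 18.3.1 names Day 7/Visit T2 at once, so only the label needs changing. The impossible end date disappears if EOS and completion are both taken as FU2, but SAP 4.1 says EOS is FU1.

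**Conclusion.** The point holds and is minor. SAP 18.2.1 uses an end of study that conflicts with SAP 4.1 and the protocol. As written, four sets of TEAE summaries pool about 13 days of full ascertainment with about 30 days of mainly SAE ascertainment: 70% of nominal days, or about 65% to 73% across the visit windows.

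A reader might take the 70% as the size of a bias. It is a calendar share only. The number of late non-serious events and the fraction missed cannot be taken from the documents, and the tables are identical if nothing starts or worsens after FU1. The analysis is descriptive, both cohorts share the window, SAP 18.1 plans no cohort comparison of safety data, and the AE listing keeps every event. The Appendix 2 defect affects only derived study days and durations (SAP 7.2).

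The conclusion assumes that EOS means FU1, as SAP 4.1 states, and that footnote c describes what the FU2 call asks. If all AEs are in fact solicited at FU2, the mixing concern largely falls away, but the label conflict and the need to state the collection rule remain.

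**What to change.** 1. Use end of study for FU1 only: correct SAP 18.2.1 and relabel the Day 7 visit in SAP 18.3.1.
2. Reconcile SAP 18.2.1 with protocol 14.4. Present the TEAE summaries through FU1, either as Day 13 exactly or with a statement that the +3-day visit window of protocol 10.3.5 applies.
3. Show events that start or worsen after FU1, through FU2, in a separate row or listing: SAEs, worsening of related AEs under follow-up, and any other reports. No event is then lost, whatever FU2 turns out to collect.
4. State what is solicited at FU2, and reconcile the Adverse event review mark with footnote c in SAP Appendix 1.
5. In SAP Appendix 2, do not let an imputed AE end date precede onset, and use the FU2 date as the anchor for events that start after FU1.

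The cost is SAP wording and one extra row or listing. No new data are needed, and SAEs stay reported through FU2.

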18.3. Safety Laboratory Evaluations

18.3.1. Safety Laboratory Evaluation

Quantitative laboratory measurements, including hematology, blood chemistry, and coagulation, will be reported with the relevant laboratory reference ranges in Conventional US units and classified as Low/Normal/High by the central lab:

- Low: below the lower limit of the laboratory reference range;
- Normal: within the laboratory reference range (upper and lower limit included); or
- High: above the upper limit of the laboratory reference range.

A list of laboratory assessments to be included in the outputs is included in [Appendix 3](#).

Quantitative lab results at baseline (pre-dose on Day 1/Visit T1) and at end of study 24 hours after the last dose on Day 6 (Day 7/Visit T2) and change from baseline values at Visit T2 will be summarized by cohort. Urinalysis is quantitative and will not be summarized.

The Modification of Diet in Renal Disease (MDRD) equation ([Levey 2006](#)) for estimated glomerular filtration rate (eGFR) will be used by the central lab,

$$\text{eGFR (mL/min/1.73 m}^2\text{)} = 175 \times (\text{serum creatinine})^{-1.154} \times (\text{Age})^{-0.203} \times 0.742 \text{ (if female)} \\ \times 1.212 \text{ (if African American), where creatinine is in mg/dL.}$$

All lab test results will be listed by subject, lab test name, and visit.

18.4. Vital Signs

The following vital signs measurements will be reported for this study:

- Sitting systolic blood pressure (mmHg)
- Sitting diastolic blood pressure (mmHg)
- Sitting heart rate (beats per minute [bpm])

Summaries will be provided by cohort for vital signs data for observed values at baseline and Visit T2 and change from baseline values at Visit T2 .

18.5. Physical Examination

Clinically significant abnormal findings that occur post initial IMP will be reported as TEAE.

All abnormalities in physical examinations will be presented in a subject listing.

APPENDIX 1. SCHEDULE OF EVENTS

Study Period	Screening Period	Treatment Period			Washout Period			SAE FU	
Visit	S1	T1	—	T2	—	—	—	FU1 ^a	FU2
Procedure	Day -42 to -1	Day 1	Day 2-4	Day 5	Day 6	Day 7 ^b	Day 8-12	Day 13 (+3 days) by phone	Day 43 (+5 days) by phone ^c
Informed consent	X								
Enrollment criteria	X	Predose							
Review of breastfeeding practice	X	Predose							
Adequate breast milk production/weaning	X	Predose	X	X					
Infant able to bottle feed	X	Predose							
Adequate stored breast milk/ formula to feed infant ^d	X	Predose	X	X	X	X			
Demographics	X								
Medical history ^e	X								
Concomitant medications	X	X	X	X	X	X	X	X	
Adverse event review	X	X	X	X	X	X	X	X	X
Physical exam	X					X			
Weight	X	X				X			
Height/BMI	X								
Vital signs ^f	X	X				X			
Serum pregnancy test	X								
Urine pregnancy test		X				X			
Urine drug and alcohol screen	X								
Randomization		X							
Pump breast milk for predose collection at CRU (\leq 1 hour before IMP administration)		X							
Lactation consultant visit (optional)	X	X	X	X		X	X	X ^g	
Pump and discard breast milk ^h		X	X	X		X ⁱ	X	X	

Phone call to subject ^j			X	X				X	X
Predose PK blood sample		X							
Clinical lab evaluations ⁿ	X	X				X			
Dispense IMP		X							
IMP administration at CRU		X			X				
Self-administration of IMP			X	X					
CRU check-in (evening) ^k				X					
IMP return ^k				X					
Study Drug Diary			X	X					
Domicile in CRU				X	X				
Pump breast milk for 0-24 hr. post-dose collection at CRU ^l					X	X			
24-hr (after Day 6 dose) PK blood sample ^m						X			
CRU Discharge (morning)						X			
BMI = body mass index; BP = blood pressure; CRU = clinical research unit; DBP = diastolic blood pressure; FU1 = follow-up visit 1; HR = heart rate; min = minutes; PK = pharmacokinetic; S1 = screening visit 1; SAE FU = serious adverse event follow-up; SBP = systolic blood pressure; T1 = treatment visit 1; T2 = treatment visit 2									
a. Subjects may resume breastfeeding. b. All procedures will be completed at early termination except 24-hour PK blood sample and breast milk collection. c. Day 43 phone call to follow-up on SAEs and question if patient was able to resume breastfeeding (if intended) without problems. d. Subjects must have adequate stored breast milk and/or infant formula available to feed the infant after the first dose of IMP through Day 13 of the study. e. In addition to existing medical conditions, medical history should include gestational age at delivery, date of delivery, stage of lactation, length of time postpartum, and smoking and alcohol intake. f. Vital signs will include DBP, SBP, and HR. Subject will rest for several minutes prior to assessments. g. Lactation consultant visit for subjects who desire to re-establish breastfeeding at the end of study (Visit FU1). h. Pump and discard breast milk after the 1st dose of IMP on Day 1 through Day 5 and Day 7 through Day 13. i. Discard breast milk produced after completion of the 24hr breast milk collection period. j. For Day 2 through Day 5, remind subject to take IMP appropriately and discard breast milk produced after Day 1. If subject misses a dose of IMP contact the Sponsor immediately. k. With sponsor approval, the subject may check-in to the CRU the morning of Day 6 and return IMP at that time. l. Breast milk collections will be performed using an electric pump at specified intervals (± 30 min) over 24 hours at 3, 6, 9, 12, 16, 20, and 24 hours following IMP dosing on Day 6. Both breasts will be emptied completely during each collection. At each sampling time point, milk collected from each breast will be mixed together and the total volume measured. Milk will be stored frozen until time of analysis. The specific timing of the milk sample relative to the IMP dose will be recorded. m. A blood sample for PK will be collected on Day 7 approximately 24 hours (± 30 min) after IMP administration on Day 6. n. Chemistry and hematology at Visit S1, Visit T1 and Visit T2; Serology and coagulation parameters at Visit S1 only.									

APPENDIX 2. PARTIAL DATE CONVENTIONS

Imputed dates will NOT be presented in the listings.

The following rules will be used to impute partial missing AE start/stop dates:

AE start date	If only Day is missing:	If the AE start year and month are the same as that for the first dose (Day 1) date, then the AE start day will be imputed as the day of first dose date; otherwise, the AE start day will be imputed as the first day of the month.
	If both Day and Month are missing:	If AE start year is the same first dose year, then the AE start Month and Day will be imputed as the Month and Day of first dose date; otherwise, the AE start date will be imputed as 01 January.
	If Year of AE start date is missing, or AE start date is complete missing:	The AE start date will be imputed as the first dose date.
AE end date	If only Day is missing:	If only Day is missing and AE end month and year are the same as the month and year of the EOS date, then use the subject completion date; otherwise, the last day of the month will be imputed.
	If both Day and Month are missing:	If both Day and Month are missing and AE end date year is the same as the year of the EOS date, then the subject completion date will be used to impute. If the year of the AE end date precedes the year of the EOS date, then the AE end month and day will be set to 31 December.
	If the Year of AE end date is missing, or AE end date is completely missing:	If only Year is missing, then the EOS year will be assigned to the end date. If the AE end date is completely missing, then “Ongoing” status will be assigned.

AE = adverse event; EOS = End-of-Study

The following rules will be used to impute partial missing medication dates:

Medication start date	If only Day is missing:	If only Day is missing, then the first day of the month will be assumed.
	If only Day and Month are missing:	If both Day and Month are missing, then January 1 will be assumed.
	If only Year is missing, or date is completely missing:	If only Year is missing, then informed consent signature year will be used to impute. If medication start date is completely missing, then the informed consent signature date or medication end date whichever is earlier, will be used to impute.
Medication end date	If only Day is missing	If only Day is missing, then the last day of the month will be assumed.
	If both Day and Month are missing	If both Day and Month are missing, then the medication end date month and day will be set to December 31.
	If Only Year is missing, or medication end date is completely missing	If only Year is missing, then the year of last visit will be assigned for the end date. If medication end date is completely missing, then “Ongoing” status will be assigned, and the end of study date will be imputed

EOS = End-of-Study

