4.1. Overview

This is a Phase 4, open-label study that will estimate the daily infant dosage and RID for BA and FCDP and characterize the excretion of ETC-1002, metabolites ESP15228, ETC-1002-glucuronide, EZE, and EZE-glucuronide in the mature breast milk of healthy women. The study will enroll 16 healthy lactating subjects, who will be randomized in a 1:1 ratio to receive either BA (Cohort 1) or FCDP (Cohort 2), who choose to stop breastfeeding their infant for the duration of the Treatment and Washout periods (13 days). After signing the informed consent form (ICF), subjects will enter the Screening Period for up to 42 days, followed by a 6-day Treatment Period and a 7-day Washout Period. At Visit T1, subjects will be administered investigational medicinal product (IMP) at the clinical research unit CRU. The IMP will then be self-administered at home on Day 2 through Day 5. Study staff will phone subjects Day 2 through Day 5 to ensure IMP is being taken appropriately and remind subjects to discard breast milk produced after the first dose of IMP. Subjects will check-in to the CRU on the evening of Day 5 (with Sponsor approval the subject may check-in to the CRU on the morning of Day 6) for Visit T2 and start a 24-hour breast milk collection after the last dose of IMP on the morning of Day 6. Serum PK samples will be obtained on Day 7, approximately 24 hours after IMP administration on Day 6. Subjects will be discharged from the CRU on the morning of Day 7 approximately 24 hours after Day 6 dosing and the completion of all Day 7 assessments. At the end of the Washout Period on Day 13, all subjects will be contacted by phone for a Post-treatment Follow-up Visit. Once the call is complete, subjects may resume feeding their infants breast milk that is currently being produced. On Day 43 (Visit FU2), study staff will contact subjects by phone to assess for SAEs and if the patient was able to resume breastfeeding (if intended).

Please refer to [Appendix 1](#) for a detailed Schedule of Assessments.

The study design is presented in [Figure 1](#).

Figure 1: Study Schematic

Screening Period: The Screening Period will begin with a Screening Visit (Visit S1) that will occur up to 42 days prior to randomization (Visit T1). Visit S1 will allow the Investigator to assess the subject's eligibility and current breastfeeding practices. After the subject provides written informed consent, the subject will undergo screening assessments as outlined in [Appendix 1](#).

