8.4.1. Imputation of Missing Dates

For adverse events, and for prior and concomitant medications, if the start and/or end dates are incomplete, then the date will appear as-is (partial or missing) in the listings. When a complete

date is needed, e.g., to compute the Study Day, imputation rules specified in [Appendix 2](#) will be used unless otherwise specified. In essence, AEs of uncertain start date will be considered as having started after the first dose of study drug. Medications of uncertain start or end dates will be considered as having started before, or continued after the first dose of study drug, respectively.

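### SAP Appendix 2 moves some incomplete AE start dates to the first-dose date without checking the end date, so an AE that ended before dosing can be counted as treatment-emergent

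*SAP*

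**What the plan says.** The AE start-date rules in SAP Appendix 2 lead to the first-dose date in three branches:

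- Day missing, month and year the same as for first dose: "then the AE start day will be imputed as the day of first dose date".
- Day and month missing, year the same as for first dose: "then the AE start Month and Day will be imputed as the Month and Day of first dose date".
- Year missing, or the whole date missing: "The AE start date will be imputed as the first dose date". This branch carries no further condition.

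In the first two branches, if the recorded month or year differs from that of first dose, the rule uses the first of the recorded month or 1 January instead. The AE end date appears in none of these rules.

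SAP Section 8.4.1 states the principle behind them without exception: "AEs of uncertain start date will be considered as having started after the first dose of study drug". SAP Section 18.2.1 defines treatment-emergent AEs as "AEs that occur or worsen after the first dose of study drug up to the end of the study" and attaches no end-date condition.

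Protocol Section 13.1.2 collects AEs "starting from signing informed consent to the end of study" and records a resolution date for each. SAP Section 4.1 says that "subjects will enter the Screening Period for up to 42 days".

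For a medication whose start date is wholly missing, Appendix 2 does consult the end date: "then the informed consent signature date or medication end date whichever is earlier, will be used to impute".

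**The concern.** Treating an AE of unknown timing as treatment-emergent is a sound cautious default. It has no purpose when the end date already shows that the event was over before the first dose, because the timing relative to dosing is then known even though the exact onset is not. In that situation the rule produces a start later than the stop and places a pre-treatment event in the incidence, severity and relationship tables of SAP Section 18.2.1. With 8 subjects per cohort, a single misplaced event can visibly change a percentage. The medication rule shows that bounding a start date by an end date was within the authors' reach.

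**Working it through.** The plan states no figure on this point, so there is nothing to reproduce. The check applies the Appendix 2 rules to dated examples. All calendar dates below are illustrative.

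**Worked cases, first dose 20 September 2023.** Day numbers follow SAP Section 7.2: event date minus first-dose date, plus 1 if the event is on or after first dose. The SAP gives no formula for AE duration; end minus start plus 1 is assumed here.

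| Case | Recorded start | Recorded end | Imputed start | Treatment-emergent? | Duration |
|---|---|---|---|---|---|
| a | Sep 2023 | 10 Sep 2023 | 20 Sep 2023 | Yes | (10 − 20) + 1 = −9 days |
| b | 2023 | 18 Aug 2023 | 20 Sep 2023 | Yes | −33 + 1 = −32 days |
| c | wholly missing | 18 Aug 2023 | 20 Sep 2023 | Yes | −33 + 1 = −32 days |
| d | Aug 2023 | 18 Aug 2023 | 1 Aug 2023 | No | (18 − 1) + 1 = 18 days |

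In case a the event starts on Study Day 1 and stops on Study Day 10 − 20 = −10. Case d shows where the rule works: only the day is missing and the start month is before the first-dose month.

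**One boundary point.** The imputed start equals the first-dose date, while the treatment-emergent definition speaks of onset after the first dose. Section 8.4.1 settles this by deeming such AEs to have started after it.

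**How often each branch fails, given an eligible event.** The documents give no rates, so this rests on assumptions: onset uniform over the 42 days before dosing; duration 1, 3 or 7 days; the event ends before dosing; first dose on each of 365 consecutive days.

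| Missing part of start date | Share misclassified as written | Share with start capped at end date |
|---|---|---|
| Day only | 26% (7-day AE) to 35% (1-day AE) | 0% |
| Day and month | 93% to 94% | 0% |
| Year or whole date | 100% | 0% |

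The 35% can be checked by hand. The average day of the month over a 365-day year is (7 × 496 + 4 × 465 + 406)/365 = 5738/365 = 15.72. On average 14.72 of the 42 screening days therefore fall in the first-dose month, and 14.72/42 = 0.35.

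These shares are conditional on an incomplete start date for an AE that began and ended before dosing. They do not estimate how often that happens.

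**Effect on a table.** One affected subject with no other treatment-emergent AE adds 1/8 = 12.5 percentage points to a cohort, or 1/16 = 6.25 points overall.

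**After the cap.** Taking the earlier of the imputed start and the AE end date, case a starts on 10 September, lasts 1 day and is not treatment-emergent. Cases b and c start on 18 August with the same result. Case d does not change.

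**The case against.** The best defence is that the treatment-emergent definition in Section 18.2.1 governs. An AE with a recorded pre-dose end neither occurred nor worsened after dosing. Section 8.4.1 calls for imputation only when a complete date is needed, and here the end date already settles the status. A careful programmer might therefore classify the event correctly. That is possible, but the written instruction points the other way: Section 8.4.1 deems such AEs to have started after the first dose, with no exception, and Appendix 2 supplies a date that agrees.

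The second defence is rarity, and it stands. Onset and resolution dates are required for each AE (Protocol Section 13.1.2), fields may not be left blank (Protocol Section 18.3), AEs are reviewed at screening and again on Day 1, and about 16 subjects are planned. Entries of not available are allowed, however, and SAP Section 7.2 itself provides for partial or missing event dates.

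A reader might infer more than the documents support:

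- *Every pre-dose AE with an incomplete start becomes treatment-emergent.* It does not; case d is handled correctly.
- *Such an event would be reported as drug-related or severe by default.* That needs a further gap. Section 18.2.1 applies those defaults only when relationship or severity is missing, and the protocol requires both to be recorded.
- *Negative durations would appear in the AE tables.* Section 18.2 plans no AE-duration summary. Section 7.2 mentions durations only in general terms.
- *The listings would hide the reversal.* Imputed dates are not shown, but Study Days based on them are, so a start on Day 1 with a stop on a negative day would be visible.

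**Conclusion.** The rule is wrong as written in the three first-dose branches, and only there. An AE with an incomplete start date in one of those branches and a recorded end before the first dose is given a start after its stop and, under Section 8.4.1, is counted as treatment-emergent. No other section of the protocol or SAP supplies the missing check.

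The consequence is small. The 12.5 and 6.25 points are maxima. They assume one affected subject, no other treatment-emergent AE in that subject, and denominators of exactly 8 and 16. Replaced subjects who were dosed stay in the Full Analysis Set, so a denominator may be larger and the effect smaller. The error over-counts treatment-emergent AEs and does not conceal any. The analyses are descriptive, and the milk and plasma pharmacokinetic endpoints do not use AE dates.

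**What to change.** Add one condition to the AE start-date rules in SAP Appendix 2, for example: *The first-dose date is imputed only if the AE end date is missing, the AE is ongoing, or the end date could fall on or after the first dose. If the complete or partial end date shows that the AE ended before the first dose, the imputed start is no later than the AE end date (for a partial end date, the end date as imputed in this appendix), and the AE is not treatment-emergent.* Put the same exception in Section 8.4.1 so that the two places agree.

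A cap at the end date works in all three branches. A rule built on the first day of the recorded month would be undefined when the whole start date is missing. The capped date serves only for classification and ordering; it does not estimate onset.

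The cost is a short text change and one line in the date derivation, with no new data. AEs whose timing relative to dosing is truly unknown keep their cautious treatment-emergent status.
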